13 MEASUREMENT OF EFFECT

13.1 Antitumor Effect

For the purposes of this study, participants should be re-evaluated for response every 8 weeks. In addition to a baseline scan, confirmatory scans should also be obtained every 8 weeks following initial documentation of objective response.

Assessment of Overall Tumor Burden

Efficacy assessment will be conducted and reported on the eCRF. For the purpose of treatment decisions in this study, tumor progression will be assessed by the treating investigator using a consistent and objective assessment of tumor response based on the Response assessment in Neuro-Oncology (RANO) Criteria. (Appendix 4).³⁷ Treatment post-progression and confirmation of progression per Immunotherapy Response Assessment in Neuro-Oncology (iRANO) Criteria (Appendix 5) is permitted for patients who are clinically stable.³⁸

The primary efficacy endpoint is ORR per RANO. Investigator assessments will be used for the ORR, DOR, PFS and OS endpoints. Objecive responses will be confirmed by an independent expert.

Efficacy assessments will be required as follows:

- Physical Exam, AE assessment (CTCAE v.4), laboratory tests (CBC, CMP, TSH) every 2 weeks for the first 8 cycles and then every 4 weeks thereafter.
- MRI of the brain w/wo gadolinium and 2HG spectroscopy every 8 weeks.

All efforts should be made to obtain brain MRI scans with 2HG MR spectroscopy. Sites unable to perform 2HG MR spectroscopy may have this requirement waived upon discussion with and approval by the CUMC PI. Additionally, if it is not feasible to obtain 2HG MR spectroscopy for a particular paitent at any specific tumor assessment timepoint, this requirement may be waived upon discussion with and approval by the CUMC PI.

Baseline Imaging

All participants will undergo gadolinium-enhanced MRI of the brain at the timepoints specified in Table 12.1-2 for baseline assessment and on study response assessment purposes.

Investigators may obtain more frequent follow-up MRI scans as medically indicated. Local radiologic assessment of tumor measurements will be used for clinical management and investigator-assessed clinical endpoints.

Participants who are unable (due to existent medical condition, ie, pacemaker or implantable cardioverter-defibrillator device) or unwilling to have a brain MRI at baseline are excluded from the study (Section 6.4).

Participants who become unable to undergo MRI imaging after enrollment may continue in the study for assessment of OS as long as there is no safety issue which would require monitoring by MRI. [SEP] Study sites will retain local access to the imaging results for safety and efficacy reading purposes. The study investigator will review the local MRI results as clinically appropriate to ensure that any potentially emergent clinical situations are addressed in a timely fashion. Clinically significant radiologic findings or changes from baseline scans will be coded as AEs or SAEs according to the criteria described below in Section 10. [SEP]

On-study Assessment of Response

Radiographic study evaluations will take place as outlined in Section 12. Baseline MRI of the brain with gadolinium and 2HG spectroscopy should be performed within 14 days prior to the first dose.

13.1.1 Definitions

Evaluable for toxicity: All participants will be evaluable for toxicity from the time of their first treatment with Nivolumab

Evaluable for objective response: Only those participants who have measurable disease present at baseline, have received at least one cycle of therapy, and have had their disease re-evaluated will be considered evaluable for response. These participants will have their response classified according to the definitions stated below. (Note: Participants who exhibit objective disease progression prior to the end of cycle 1 will also be considered evaluable.)

Evaluable Non-Target Disease Response: Participants who have lesions present at baseline that are evaluable but do not meet the definitions of measurable disease, have received at least one cycle of therapy, and have had their disease re-evaluated will be considered evaluable for non-target disease. The response assessment is based on the presence, absence, or unequivocal progression of the lesions.

13.2 Disease Parameters

Assessment of Overall Tumor Burden and Measurable Disease

To serially evaluate tumor response to therapy, it is necessary to estimate the overall tumor burden at baseline and use this as a comparator for subsequent measurements. Measurable disease is defined by the presence of at least one measurable enhancing tumor lesion 10mm x 10mm in size on T1 post-contrast MRI of the brain. Patients with non-enhancing measurable disease may be eligible upon discussion with and approval by the CUMC PI.

Methods for Evaluation of Measurable Disease

All measurements should be taken using a ruler and recorded in metric notation. All baseline evaluations should be performed as closely as possible to the beginning of treatment and never more than 14 days before the beginning of the treatment.

The same method of assessment and the same technique should be used to characterize each identified and reported lesion at baseline and during follow-up.

Selection of Target and Non-target Lesions at Baseline:

- At baseline, all sites of disease should be classified as either measurable or non- measurable. The measurable lesions will be source for selection of target lesions for serial quantitative analysis during the study.
- Measurable and non-measurable lesions are classified according to the following characteristics:
 - Measurable Lesions
 - Contrast-enhancing (T1-weighted) lesions with clearly defined, bi-dimensionally measurable margins with minimum size of ≥ 10 mm in two perpendicular diameters.
 - In the event the MRI is performed with slices greater than 5 mm (with 0 mm skip/gap), the minimum size requirement for a measurable lesion at baseline should be two times the slice thickness.
 - It is also recommended that the same criterion be applied to a third axis, if possible, in order to consider the lesion to be a measurable lesion (e.g., visible on at least two axial slices with 5 mm thickness and 0 mm skip/gap, or two times the slice thickness).
 - Tumor around cystic or surgical cavities should generally not be considered measurable unless there is a nodular component measuring $\geq 10 \times 10$ mm. The cystic or surgical cavity itself should not be measured.
 - Measurable lesions will serve as the source of target lesions.
 - If there are multiple measurable lesions, up to 5 (at least 2) should be selected as target lesions. These lesions should generally be the largest or most reproducible tumor masses. They should lend themselves to precise anatomical re-location, tend to be the most reliably measured and be most representative of the patient's disease.

- Non-measurable Lesions
 - Non-enhancing (seen on FLAIR/T2)
 - All non-measurable enhancing lesions:
 - Smaller than 10 mm in any one diameter
 - Measurable in only one diameter
 - Not likely to be reliably visualized/measured throughout study (due to artifacts, difficult anatomy, etc.)
 - Hemorrhagic or predominantly necrotic
 - Tumor around a cyst or surgical cavity unless a nodular component > 10 × 10 mm
- Non-target Lesions
 - All measurable enhancing lesions not selected as target lesions (including those beyond upper limit of 5)
 - All non-measurable lesions

13.3 Response Criteria

For the purpose of treatment decisions in this study, tumor progression will be assessed by the treating investigator using a consistent and objective assessment of tumor response based on the Response assessment in Neuro-Oncology (RANO) Criteria (see Appendix 4).³⁷ Treatment post-progression and confirmation of progression per Immunotherapy Response Assessment in Neuro-Oncology (iRANO) Criteria is permitted for patients who are clinically stable (see Appendix 5).³⁸

Response/Progression Categories (RANO criteria):

- **Complete response (CR).** All of the following criteria must be met:
 - Complete disappearance of all enhancing measurable and non-measurable disease sustained for at least 4 weeks. In the absence of a confirming scan 4 weeks later, this scan will be considered only stable disease.
 - No new lesions.
 - All measurable and non-measurable lesions must be assessed using the same techniques as baseline.
 - Patients must be on no steroids or on physiologic replacement doses only.
 - Stable or improved non-enhancing (T2/FLAIR) lesions
 - Stable or improved clinically, for clinical signs and symptoms present at baseline and recorded to be disease related

Patients with residual non-measurable disease cannot have a complete response.
The best response possible is stable disease.
- **Partial response (PR).** All of the following criteria must be met:

- Greater than or equal to 50% decrease compared to baseline in the sum of products of perpendicular diameters of all measurable enhancing lesions sustained for at least 4 weeks. In the absence of a confirming scan 4 weeks later, this scan will be considered only stable disease.
- No progression of non-measurable disease.
- No new lesions.
- All measurable and non-measurable lesions must be assessed using the same techniques as baseline.
- The steroid dose at the time of the scan evaluation should be no greater than the dose at time of baseline scan.
- Stable or improved non-enhancing (T2/FLAIR) lesions on same or lower dose of corticosteroids compared to baseline scan.
- Stable or improved, for clinical signs and symptoms present at baseline and recorded to be disease related clinically.
- Patients with non-measurable disease cannot have a partial response. The best response possible is stable disease.

- **Progressive disease (PD).** Any of the following criterion must be met:
 - > 25% increase in sum of the products of perpendicular diameters of enhancing lesions (over best response [smallest tumor size] or baseline if no decrease) on stable or increasing doses of corticosteroids
 - Any new enhancing measurable lesion that when added to the change in initial tumor(s) exceeds a 25% increase in cross-sectional area.
 - Clear clinical deterioration not attributable to other causes apart from the tumor (e.g. seizures, medication side effects, complications of therapy, cerebrovascular events, infection, etc.). The definition of clinical deterioration is left to the discretion of the investigator but it is recommended that a decline in the Karnofsky Performance Score (KPS) from 100 or 90 to 70 or less, a decline in KPS of at least 20 from 80 or less, or a decline in KPS from any baseline to 50 or less, for at least 7 days, be considered neurologic deterioration, unless attributable to co-morbid events or changes in corticosteroid dose.
 - Failure to return for evaluation due to death or deteriorating condition
 - Classification of progressive disease may be deferred for up to three months for patients with initial radiographic findings consistent with progressive disease (criteria a and b above) as detailed below. However, if follow-up imaging after three months confirms progression or if the patient experiences significant clinical decline at any time, the date of actual progression will be back-dated to the first date that the patient met criteria for progression and such patients should discontinue further immunotherapy.

- **Stable disease (SD).** All of the following criteria must be met:
 - Does not qualify for CR, PR, or progression.
 - All measurable and non-measurable sites must be assessed using the same techniques as baseline.
 - Stable clinically.
- **Unknown response status.** Progressive disease has not been documented and one or more measurable or non-measurable lesions have not been assessed.

Table 13.1 RANO Response Criteria Summary

	CR	PR	SD	PD#
T1 + Gd	None	≥50% decrease	<50% decrease to <25% increase	≥25% increase (including new lesions)*
T2/FLAIR	Stable/Decrease	Stable/Decrease	N/A	N/A
New Lesion	None	None	None	Present (contributing to lesion size)*
Corticosteroids	None	Stable/Decreased	Stable/Decreased	Stable/Increasing
Clinical Status	Stable or Improved	Stable or Improved	Stable or Improved	Clinical decline*
Requirement for Response	All	All	All	Any*

CR = complete response; PR = partial response; SD = stable disease; PD = progressive disease; N/A = not applicable

#: Progression occurs when any of the criteria with * is present; radiologic confirmation of progression is permitted as described below

Increase in corticosteroids alone will not be taken into account in determining progression in the absence of persistent clinical deterioration.

The iRANO criteria call for serial radiographic evaluation of lesions with comparative analysis of changes in the area of contrast enhancement and nonenhancing component. Corticosteroid dosing and clinical status also contribute to response assessment. The guidance below is provided to facilitate assessment of tumor response by the treating investigator or responsible site staff.

Complete Response (CR): Requires all of the following:

- Complete disappearance of all enhancing measurable and non-measurable disease confirmed on consecutive scans at least four (4) weeks apart
- Stable or improved non-enhancing (T2/FLAIR) lesions,
- No new lesions,
- Off corticosteroids (or on physiologic replacement doses [up to the equivalent of 20 mg/day of hydrocortisone]), and

- Stable or improved clinical status.

Partial Response (PR): Requires all of the following:

- $\geq 50\%$ decrease compared with baseline in the sum of the products of the diameter (SPD) of measurable enhancing target lesions confirmed on consecutive scans at least four (4) weeks apart
- No progression of non-target disease (enhancing and non-enhancing (T2/FLAIR) lesions),
- No new lesions,
- Corticosteroid dose stable ($< 10\%$ increase) or decreased, and
- Stable or improved clinical status.

Stable Disease (SD): Requires all of the following:

- Does not qualify for CR, PR or PD,
- Stable nonenhancing (T2/FLAIR) lesions
- Corticosteroid dose NOT increased by $\geq 50\%$, and
- Stable or improved clinical status.
- Patients with non-measurable disease only cannot be assessed as a CR. The best possible response is stable disease (SD).

Progressive Disease (PD): Defined by any of the following:

- $\geq 25\%$ increase in the SPD of measurable enhancing (target) lesions plus > 5 mm absolute increase in the sum of the longest diameters (SLD) of target lesions compared to the best response after initiation of therapy (nadir), or baseline if the baseline is the nadir value,²
- Clear progression of enhancing non-target disease
- Significant increase in T2/FLAIR non-enhancing lesions not caused by co-morbid events (e.g., radiation therapy, demyelination, ischemic injury, infection, seizures, post-operative changes, or other treatment effects)
- Any new lesions or
- Clear clinical deterioration not attributable to other causes apart from the tumor (e.g., seizures, medication adverse effects, complications of therapy, cerebrovascular events, infection and so on) or changes in corticosteroid dose.
- Increasing steroid doses alone do not constitute PD.

Patients who have imaging findings that meet criteria for progressive disease more than 6 months from starting immunotherapy are expected to have a low likelihood of ultimately deriving clinical benefit and should discontinue therapy. For patients who have imaging findings that meet criteria for progressive disease within 6 months of starting immunotherapy including patients who develop new lesions but who do not have substantial neurological decline, confirmation of radiographic progression by follow-up MRIs should be sought following an

interval of up to 3 months after initial radiographic evidence of progressive disease to decrease the likelihood of prematurely declaring progressive disease in patients with pseudoprogression or delayed response.

Patients who develop substantial new or worsened neurological deficits not due to comorbid events or a change in co-administered medication at any time within the 3-month follow-up window should discontinue immunotherapy. For these patients, the date of actual tumor progression should be back-dated to the date when radiographic progressive disease was initially identified. Those with confirmation of further radiographic progression based on a comparison with the scan that first showed evidence of disease progression, or who develop substantial clinical decline at any time, should also be classified as having progressive disease with the date of disease progression back-dated to the first date that the patient met criteria for radiographic progression. In the event that follow-up imaging does not confirm further disease progression compared with the scan of the tumor that first showed initial progressive changes, but instead there is stabilization or reduction in tumor burden, treatment should be continued or resumed in the absence of increased corticosteroid dosing.

In addition, in uncertain cases in which acquisition of tumor histopathology by biopsy or resection is thought to be feasible, pathological assessment might be considered to clarify the cause of progressive imaging findings. If pathology confirms a predominance of recurrent tumor, the cause should be considered to be true progression. For cases where there is no evidence of a viable tumor, or where a prominence of gliosis or inflammation with restricted viable tumor is reported, the cause should be deemed consistent with treatment effect, and such patients should be classified as stable and allowed to continue therapy.

Unable to Evaluate (UE): Defined by any of the following:

- A patient's corticosteroid dosage has increased within 2 weeks of MRI assessment relative to the dose taken at the time of the previous assessment, cannot be classified as having a complete response, partial response, or stable disease and should be classified as non-evaluable at that time point. Conversely, patients who decrease corticosteroid use within 2 weeks of MRI assessment relative to the dose taken at the time of the previous assessment cannot be classified as having progressive disease and should be classified as nonevaluable.
- Radiographic changes indicative of progression are suspected due to other causes, including decreased steroid doses. Note: In contrast, if clinical deterioration occurs but is attributed to other causes, the time point response should be assessed with consideration to radiographic response and steroid use.
- Any target and/or non-target lesion present at baseline becomes unevaluable, including surgical removal of any target and/or non-target lesion. Note: PD can be determined without evaluation of all sites of disease based on the SPD for target lesions, evaluation of unequivocal progression in non-target lesions or observation of a new lesion within the available radiographic or clinical assessments.

Columbia University Medical Center
Herbert Irving Comprehensive Cancer Center
Version Date: January 30, 2024

Patients with stable or improved imaging studies, whose corticosteroid dose was increased by $\geq 50\%$ should be considered unevaluable (UE). They should be observed closely. If their corticosteroid dose can be reduced back to the baseline dose, they may continue being followed for response. If further clinical deterioration related to tumor or radiographic progression becomes apparent, the date of progression should be the date when the average daily corticosteroid dosage for the seven day period increased $\geq 50\%$ as compared to baseline.

Table 13.2 iRANO Response Criteria Summary

	CR	PR	SD	PD
T1 + Gd	Complete disappearance	$\geq 50\%$ decrease from baseline in SPD	Insufficient change in SPD to meet criteria for CR, PR or PD	$\geq 25\%$ increase and $>5\text{mm}$ increase in SLD from baseline
Non-target disease: Enhancing Non-Enhancing	Stable/Decrease**	Stable/Decrease	Stable/Decrease	Increased, not due to other causes
New Lesion	None	None	None	Present
Corticosteroids	None	Stable/Decreased	Stable/Decreased	A $\geq 50\%$ increase in steroid dose alone will not constitute PD (unless later confirmed PD)
Clinical Status	Stable or Improved	Stable or Improved	Stable or Improved	Clinical decline
Requirement for Response	All of the above; Response must be confirmed on consecutive scans at least 4 weeks apart	All of the above; Response must be confirmed on consecutive scans at least 4 weeks apart	All of the above	Progression of disease occurs when PD is present in any category. For patients who have imaging findings that meet criteria for progressive disease within 6 months of starting immunotherapy, a window of up to 3 months may be allowed to confirm progression.

CR = complete response; PR = partial response; SD = stable disease; PD = progressive disease

** To qualify for CR there should be complete disappearance of enhancing non-target disease, but there can be stable or decreased residual non-enhancing FLAIR disease.

Evaluation of Target Lesions

Columbia University Medical Center
Herbert Irving Comprehensive Cancer Center
Version Date: January 30, 2024

Complete Response (CR): Disappearance of all enhancing disease (measurable and non-measurable) sustained for at least 4 weeks with stable or improved non enhancing FLAIR/T2 lesions. No new lesions. Clinically, participants must be stable or improved and not on corticosteroids exceeding physiologic replacement doses.

Partial Response (PR): 50% or more decrease of all measurable enhancing lesions sustained for at least 4 weeks with no progression of non-measurable disease and stable or improved non enhancing FLAIR/T2 lesions. No new lesions. Clinically, participants must be stable or improved and on stable or reduced dose of corticosteroids compared to baseline.

Progressive Disease (PD): 25% or more increase in enhancing lesions despite stable or increasing steroid dose, increase (significant) in non-enhancing T2/FLAIR lesions, not attributable to other non-tumour causes, or any new lesions. Clinical deterioration (not attributable to other non-tumour causes and not due to steroid decrease).

Stable Disease (SD): Does not qualify for complete response, partial response or progression with stable non-enhancing FLAIR/T2 lesions. Clinically, participants are stable and are on stable or reduced dose or corticosteroids compared to baseline.

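### Section 13.3 as written bars a partial response in anyone with non-measurable disease, against its own PR list and tables, and 15.4 does not cite the 13.4 criteria for the primary ORR

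*Combined protocol and SAP*

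**What the plan says.** The primary endpoint is ORR, meaning confirmed CR plus PR, tested against 10% with an exact test (15.2, 15.4).

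- **PR list, 13.3.** It requires a decrease of at least 50% in measurable enhancing disease, "No progression of non-measurable disease" and "Stable or improved non-enhancing (T2/FLAIR) lesions". Its last item is "Patients with non-measurable disease cannot have a partial response. The best response possible is stable disease".
- **CR list, 13.3.** It requires all enhancing disease, measurable or not, to disappear, and it accepts stable T2/FLAIR lesions. It then adds "Patients with residual non-measurable disease cannot have a complete response" and puts the best response for such patients at SD.
- **Definitions, 13.2.** The non-measurable class begins with "Non-enhancing (seen on FLAIR/T2" and goes on to enhancing lesions under 10 mm in any one diameter, among others. Non-target disease includes "All non-measurable lesions".
- **Non-enhancing participants.** Sections 6.1 and 13.2 let patients with non-enhancing measurable disease enter with the approval of the lead-site principal investigator. Section 13.4 assesses those with only non-enhancing lesions by the low-grade glioma RANO criteria, which include CR and PR.
- **Primary analysis, 15.4.** PR and CR are to follow RANO, with a pointer to 13.3 alone.

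**The concern.** The PR list asks that non-measurable disease should not progress and that T2/FLAIR lesions should be stable or better. Both items assume a partial responder can have such disease. The closing sentence then denies PR to anyone who has it. A reviewer who follows that sentence and the 13.2 definitions would record SD for a patient who meets every other PR criterion, and a reviewer who follows the tables would record PR. One set of scans then gives two responder states for the primary endpoint.

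The sponsor-investigator or a designee reviews all responses (13.7, 15.4). That makes scoring uniform but does not say which sentence governs. In an open-label single-arm trial, settling the conflict after the scans have been seen would invite the criticism that the results drove the choice.

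**Working it through.** **1. The passages side by side**, for a patient with measurable enhancing tumour, a confirmed shrinkage of at least 50%, stable T2/FLAIR lesions and all other PR conditions met:

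| Place | Response |
|---|---|
| 13.3, PR list without its last item | PR |
| 13.3, last item of the PR list | SD at best |
| Table 13.1, T2/FLAIR row | PR (stable or decreased is accepted) |
| 13.3, Evaluation of Target Lesions | PR: "50% or more decrease of all measurable enhancing lesions sustained for at least 4 weeks with no progression of non-measurable disease" |
| Table 13.3, target PR with non-target Non-CR/Non-PD | PR |

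The cap stands alone against four other places. The iRANO text in 13.3 has a similar sentence about CR, and there it is limited to patients with non-measurable disease *only*.

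**2. The CR sentence.** Take a patient whose target lesions have gone but who keeps a small non-measurable enhancing lesion. CR is ruled out everywhere. The sentence in 13.3 then gives SD at best, while Table 13.3 gives PR for target CR with non-target Non-CR/Non-PD. Responder status differs.

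**3. The 13.4 participants.** Section 13.4 gives them CR and PR, but 15.4 points to 13.3. Section 13.1.1 requires measurable disease for response evaluability. Section 13.2 first defines that as enhancing and then speaks of non-enhancing measurable disease. Section 15.7 puts all eligible participants in the main analysis.

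**4. The plan's own figure.** Inputs from 15.2: null 10%, alternative 30%, one-sided alpha 0.05, beta 0.10. The rule is to reject if X ≥ c, with c the smallest count for which P(X ≥ c | n, 0.10) ≤ 0.05.

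- n = 33: c = 7, alpha 0.0417, power P(X ≥ 7 | 33, 0.30) = 0.9056.
- n = 32: c = 7, power 0.8869, below 0.90.

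So 33 is the smallest adequate size, and 33/0.9 = 36.7, rounded up to 37. Both stated figures reproduce.

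**5. One misread responder, n = 33.** 7/33 gives p = 0.042 (reject) and 6/33 gives p = 0.106 (do not reject). The decision changes only if the correct count is exactly 7. P(X = 7 | 33, 0.30) = 0.088.

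**6. The cap applied literally to k of 33.** Assumption: none of the k can count as a responder, and the other 33 − k respond at 30%. Power = P(X ≥ 7 | 33 − k, 0.30). The documents give no k, so it is varied.

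| k | Power |
|---|---|
| 0 | 0.9056 |
| 1 | 0.8869 |
| 3 | 0.8405 |
| 5 | 0.7798 |
| 10 | 0.5601 |

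**7. Denominator.** Seven responders give p = 0.048 in 34, 0.055 in 35 and 0.071 in 37. Who is counted can therefore also change the decision.

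**The case against.** The best defence is that the cap is a visible drafting slip. The list it closes and three other places allow PR, so an experienced reviewer would not apply it literally. Very probably so, and that is why no actual loss of responders is predicted here. The sentence is still a stated rule for the primary endpoint, and nothing in the documents ranks it below the others.

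Three stronger readings are tempting, and the documents do not support them.

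- **That no PR could be recorded at all.** This needs every participant to have T2/FLAIR or other non-measurable disease and every reviewer to follow the one sentence. The documents give no such count.
- **That a patient whose enhancing disease has all gone, with stable T2/FLAIR, is CR, PR or SD depending on the page.** The first CR criterion concerns enhancing disease and the list accepts stable T2/FLAIR, so residual disease in the CR sentence most naturally means enhancing disease. The Table 13.2 footnote, written for iRANO, agrees. Only the conflict in step 2 remains.
- **That 13.4 participants are shut out of the ORR.** Section 13.4 says its criteria will be used, 13.1 sets the endpoint as ORR by RANO, the eligibility exception speaks of measurable non-enhancing disease, and 15.7 keeps all eligible participants. A word seems to be absent from the 15.4 sentence on criteria and may have been lost in reading the PDF. What remains is mainly a missing cross-reference.

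**Conclusion.** The point holds as an error of wording in the definition of the primary endpoint, and it should be fixed. The PR cap is wrong as written, the SD clause after the CR sentence conflicts with Table 13.3 for residual non-measurable enhancing disease, and 15.4 does not carry the 13.4 criteria into the ORR.

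The size depends on how the cap is read. If it is treated as a slip, the effect is close to nil. If a single responder is misread, only a result of exactly 7 of 33 is at risk. If the cap is applied literally to several participants, the loss is not confined to results near the cut-off: power is about 84% at k = 3, 78% at k = 5 and 56% at k = 10. These are sensitivity values for an assumed k and not forecasts. They rest on 33 analysed, a cut-off of 7 and a true ORR of 30% in the participants not capped.

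**What to change.** Before responses are adjudicated:

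1. In the last item of the PR list in 13.3, insert *only* after *disease*. State there, and at the matching iRANO line, that the cap does not apply to participants assessed under 13.4. Without that exception the corrected cap would itself clash with 13.4, because 13.2 lists non-enhancing lesions as non-measurable.
2. Replace the SD clause after the CR sentence, so that residual non-measurable enhancing disease rules out CR but not PR, as Table 13.3 already has it.
3. In 15.4, define ORR as confirmed CR or PR by 13.3, or by 13.4 for participants with only non-enhancing lesions. Say that such eligible participants are evaluable under 13.1.1 and stay in the denominator, consistent with 15.7.

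The cost is a few sentences in an amendment. It needs no new scans or participants and no change to 33 or 37.
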